#### 7. ASSESSMENT AND FOLLOW-UP OF SUBJECTS

#### 7.1 DEFINITION OF END OF TRIAL

The trial is defined as ended when the last randomised participant has a final assessment performed or the last participant withdraws from the trial.

#### Questionnaire assessments at 3 and 6 months

All subjects will be posted questionnaires to complete and return in stamped addressed envelopes at 3 and at 6 months following randomisation. The questionnaire will consist of: AQLQ, Asthma Control Questionnaire, HAD

questionnaire, EQ5D, Treatment experience and adherence questions (and respondent costs questionnaire at 3 months only). Those not returning the questionnaires after 3 weeks will receive a single postal reminder followed 1 week later by a single telephone call or email from the study team. The participant will be offered the opportunity to complete the mini AQLQ questionnaire over the telephone at this point.

NB- As detailed in the Patient Information Sheet, participants medical records and data collected for the study will be looked at by authorised persons from the University of Aberdeen and University of Southampton Clinical trials Unit.

All telephone calls will be carried out in a private environment by nominated UoSCTU staff with the required authorisation permissions in place.

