**BREATHE** 

Visit:	Pre screen	Baseline assessment	3 physio sessions, 2 weekly intervals	6-8 weeks post baseline	3 month Follow up postal questionnaire s	6 month Follow up postal questionnaire s	12 month Follow up visit With study nurse
Physiological measurements: Spirometry and FENO		х					х
Randomisation		X					
Provision of DVD & 'Booklet' Group 1		x					
Face-to-face Physiotherapy			х				
Process Evaluation Telephone interview for 12 to 15 patients in each group				х			
Medical Notes Review							х
Adverse Events		х	х		х	х	Х

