#### 5. STUDY INTERVENTION

#### 5.1 TREATMENT ARMS

We propose a prospective evaluation of a physiotherapy breathing retraining programme (already shown to be effective in face-to-face contact) delivered in a new DVD format. If effective, this could be used in routine NHS asthma care. The DVD breathing instruction programme will be developed in phase 1 of the project. In the subsequent randomised controlled trial (phase 2), we will assess the effectiveness of this DVD as adjuvant treatment for asthmatic adults with asthma-related health status impairment (AQLQ <5.5) despite pharmacotherapy. Consenting subjects will be randomly assigned to

- Arm A: Receipt of the DVD, (plus supporting written material)
- Arm B: Usual care
- Arm C: 3 sessions of 'face-to-face' physiotherapy breathing instruction (plus supporting written material)

In all 3 arms, no attempt will be made to change the standard asthma care provided in the practice.

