#### 6.3.2 Non serious Adverse Events

All adverse events that may be related to the study will be recorded in the relevant case report form and Adverse Event form and sent to the UoSCTU within one month of the form being due. As adults on average see their GP approximately 5 times per year for a variety of routine and unscheduled appointments (e.g. for medication review, self-limiting minor illnesses and long-term conditions unrelated to asthma), many medical encounters are of no relevance to the study. Events that will be recorded include any judged by the study nurse to be possibly related to the study. In particular, all medical encounters related to the following medical areas or symptoms will be recorded in the Adverse Events form:

**Psychological morbidity:** any events relating to anxiety, depression or mood disorders

**Respiratory morbidity**: any events relating to breathing or chest symptoms

**Musculoskeletal, Abdominal and chest pain:** any events relating to pain in these systems unless known to be associated with an unrelated pre-existing condition.

The study nurses are advised to record any event for which there is uncertainty as to whether it is study related or not, and to discuss with the local PI or CI.

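### Adverse events are scheduled at 3 and 6 months in every arm, but the listed postal pack has no item to collect them, while face-to-face alone has three extra collection points

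*Protocol*

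**What the plan says.** **Schedule of Observations and Procedures.** The row "Adverse Events" is marked at baseline, in the column "3 physio sessions, 2 weekly intervals", and at 3, 6 and 12 months. It is blank at pre-screening and at the 6-8 week interview. A separate row, "Medical Notes Review", is marked at 12 months and is not limited to any arm.

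**Section 5.1.** Only Arm C receives "3 sessions of 'face-to-face' physiotherapy breathing instruction (plus supporting written material"). Arms A (DVD) and B (usual care) have no treatment sessions.

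**Section 7, 3 and 6 months.** The packs go to everyone: "All subjects will be posted questionnaires to complete and return in stamped addressed envelopes at 3 and at 6 months following randomisation". The listed contents are the AQLQ, the Asthma Control Questionnaire and the HAD "questionnaire, EQ5D, Treatment experience and adherence questions (and respondent costs questionnaire at 3 months only"). The questionnaire rows of the schedule name no adverse event form at these times either. Non-responders get a reminder and then a call or email, at which only the mini-AQLQ is offered by telephone.

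**Section 6.3.2.** The study nurse decides what counts: "Events that will be recorded include any judged by the study nurse to be possibly related to the study". There is also a rule that does not depend on arm: "In particular, all medical encounters related to the following medical areas or symptoms will be recorded in the Adverse Events form". The areas are psychological, respiratory, and musculoskeletal, abdominal or chest pain.

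**The concern.** Two features combine. First, the schedule promises adverse event collection at 3 and 6 months, but Section 7 gives no means of doing it: no item in the pack, no nurse contact between baseline and month 12, and no one described as completing an adverse event form at those times. Second, the only other scheduled collection between baseline and month 12 is at the physiotherapy sessions, which one arm has and two do not.

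What is at stake is the descriptive safety comparison for mild, non-serious events. Serious events and events that bring a participant to a clinician have other routes into the record. A symptom brought on by the exercises that the participant never takes to the GP may be mentioned to a physiotherapist and otherwise go unrecorded. Section 3 itself foresees symptoms that the exercises seem to provoke, since the DVD and booklet are to explain how to manage them. It also says that the research centres on the DVD because that is the format most likely to enter routine care. If few mild events are recorded with home use of the DVD, the reader should be able to tell whether few occurred or few were asked about.

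**Working it through.** The protocol gives no adverse event rate or related power figure, so there is nothing to reproduce. The check is a count of scheduled collection points after baseline, followed by an illustration on assumed capture rates.

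**Inputs**
- Schedule marks after baseline: physiotherapy column, 3, 6 and 12 months.
- Sessions in that column: 3, in Arm C only (Section 5.1). The single mark is taken to apply to each session.
- Postal packs: all arms, no adverse event item listed (Section 7).

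**Count**

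| Reading | Face-to-face | DVD | Usual care |
|---|---|---|---|
| Every mark carried out | 3 + 1 + 1 + 1 = 6 | 1 + 1 + 1 = 3 | 3 |
| Pack exactly as listed | 3 + 0 + 0 + 1 = 4 | 0 + 0 + 1 = 1 | 1 |

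Face-to-face has three more on either reading.

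**Illustration.** Suppose true risk is equal in all arms and each collection point captures a given event with probability c. With k points the chance of capture is 1 − (1 − c)^k. The values of c are assumptions.

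| c | k = 6 v 3 | Ratio | k = 4 v 1 | Ratio |
|---|---|---|---|---|
| 0.1 | 46.9% v 27.1% | 1.73 | 34.4% v 10.0% | 3.44 |
| 0.3 | 88.2% v 65.7% | 1.34 | 76.0% v 30.0% | 2.53 |
| 0.5 | 98.4% v 87.5% | 1.12 | 93.8% v 50.0% | 1.88 |

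For example, at c = 0.1: 1 − 0.9^6 = 0.469 and 1 − 0.9^3 = 0.271, ratio 1.73; 1 − 0.9^4 = 0.344 against 0.100, ratio 3.44.

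These ratios lie at the upper end. Every point is treated as able to capture any event, including one that has not yet happened, and the all-arm notes review is left out. The table shows two things only: the direction of the imbalance, and that giving the 3- and 6-month marks a working route brings the ratio closer to 1 at each assumed c. It does not estimate the imbalance in this trial.

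**The case against.** The strongest reply is that this is a documentation mismatch rather than a plan to leave events uncollected. Section 7's list for the 12-month visit likewise omits adverse events and the notes review, although the schedule marks both, so these lists are evidently not exhaustive. Section 6.3.2 places events on a case report form and an Adverse Event form, separate from the outcome questionnaires. Nothing instructs physiotherapists to ask about events, so one mark should not be read as active questioning while identical marks at 3 and 6 months are read as empty. The medical-encounter rule, the blinded 12-month nurse and the notes review apply to every arm. HAD, ACQ and mini-AQLQ scores track mood and respiratory worsening in all arms at 3, 6 and 12 months. Adverse events are not a listed outcome, and no between-arm test of them is planned.

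Much of this stands. A reader might infer that harms are over-counted in face-to-face, but extra contacts record real events more fully and do not create false ones. A reader might also infer that DVD harms are missed, or not sought until month 12. The schedule plans collection at 3 and 6 months in every arm, the all-arm sources remain, and usual care is affected as much as the DVD.

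The reply does not remove two facts. Even with every mark honoured, the count is 6 v 3 v 3. And for the postal time points no instrument, person or route is described, whereas the 12-month mark at least coincides with a planned nurse visit. The shared sources are also weak for mild events. The notes review and encounter rule need a medical encounter, the 12-month visit relies on recall of up to a year, and those who do not respond to the visit invitation may complete its questionnaires by post. The treatment experience questionnaire is scheduled at 3 months for the two active arms only, so it cannot serve a three-arm comparison.

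**Conclusion.** The point holds in a limited form. The schedule and Section 7 do not fit together on adverse events at 3 and 6 months, and face-to-face alone has three additional collection points. Capture of mild non-serious events that do not lead to a medical encounter may therefore be fuller in face-to-face than in the DVD and usual care arms. The count is 6 v 3 v 3, or 4 v 1 v 1 if the packs are as listed. It assumes that the physiotherapy mark applies to all three sessions and that the 12-month visit takes place.

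The size of any resulting difference in recorded events cannot be derived from the protocol. A reader might infer a two- to four-fold spurious difference, for instance by assuming 80% capture at sessions against 20-40% elsewhere. That is only the ratio of the assumed rates (80/40 = 2, 80/20 = 4), and it gives the scheduled 3- and 6-month collection no credit. The effect is confined to the descriptive safety comparison. The primary AQLQ analysis and the conclusions on equivalence and superiority are untouched. The point is still worth acting on, because mild events not asked about at the time may not be recoverable later.

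**What to change.** 1. Reconcile the schedule with Section 7 by adding one adverse event item, worded identically for all three arms, to the 3- and 6-month packs. It should cover the areas already named in Section 6.3.2: mood, breathing and chest symptoms, and pain.
2. State that any between-arm summary of adverse events uses only sources common to all arms: the postal item, the 12-month visit and the notes review.
3. List events reported only at physiotherapy sessions separately, so that they are kept but do not enter the comparison.

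The cost is one item in questionnaires already being posted and a sentence or two in the protocol. The downside is slightly more burden on respondents and more minor events for the trials unit to process. The extra session contacts in face-to-face remain, since they belong to that intervention. The change gives the three arms a shared basis for comparison and does not remove the sessions.

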#### Health economic evaluation

The resources needed to design and develop the DVD intervention will be recorded during phase 1. During the trial we will also record all resources required to provide the interventions in the DVD and the 'face-to-face' physiotherapy groups. Information will also be collected on all asthma-related healthcare costs for the 1-year follow up period. These will be collected using medical records to collect all asthma related NHS service use (primary and secondary care patient contacts, investigations and prescriptions) with maximum possible use of electronic records, supplemented where necessary by paper records. Respondent questionnaires will be completed at 3 month and 12 month data collection points to quantify time off work/college; and out of pocket expenses. This will constitute a societal perspective to the analysis.

Resources will be costed using appropriate local and national cost data. Total NHS and societal costs will be estimated for each group allowing estimates of the incremental costs of the breathing DVD and 'face-to-face' physiotherapy programmes compared to usual care. Health related quality of life will be assessed using the EuroQol (EQ5D) collected at baseline, 3, 6, and 12- months. These EQ5D scores will be used to generate quality adjusted life years (QALYs). No mortality differences are expected. The superiority analyses will include a cost-utility study (cost per QALY) and cost-effectiveness (cost per significant change in asthma-related health status, i.e. a change of 0.5 in the AQLQ score). If non-inferiority is proven between the face-to-face and DVD interventions, cost minimisation will be carried out. Where appropriate, incremental costeffectiveness ratios (ICERs) and cost-effectiveness acceptability curves (CEACs) will be estimated. Sensitivity analysis will be used to test any major assumptions made in the costing/analysis process. We will check for the extent of missing data at the analysis stage. If considered necessary, we will use appropriate statistical methods (for example multiple imputation) to impute missing data. This will be presented as a sensitivity analysis, i.e. in addition to the complete case analysis.

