#### Summary:

We aim to analyse 210 in each of the DVD and usual care arms and 105 in the face-to-face breathing retraining arm). Assuming a 10% dropout rate, we will therefore aim to recruit a total sample size of 585 patients (234 in each of the DVD and 'usual care' arms and 117 in the 'face-to-face' physiotherapy arm).

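### The 3- and 6-month telephone fallback collects the mini-AQLQ but not the EQ-5D, so under a complete-case rule participants who respond only by telephone would leave the cost-per-QALY result

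*Protocol*

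**What the plan says.** Protocol section 7, Questionnaire assessments at 3 and 6 months, posts the AQLQ, the ACQ and the HAD, together with the "questionnaire, EQ5D, Treatment experience and adherence questions (and respondent costs questionnaire at 3 months only"). Those who have not replied after three weeks "will receive a single postal reminder followed 1 week later by a single telephone call or email from the study team". The section then adds: "The participant will be offered the opportunity to complete the mini AQLQ questionnaire over the telephone at this point". No other part of the protocol offers the EQ-5D by telephone.

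At 12 months the fallback is wider. Under the final assessment visit heading, non-responders may complete that visit's questionnaires by post, and these include the EuroQol.

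The Health economic evaluation in the same section states: "Health related quality of life will be assessed using the EuroQol (EQ5D) collected at baseline, 3, 6, and 12- months". It continues: "These EQ5D scores will be used to generate quality adjusted life years (QALYs"). On missing data it says: "If considered necessary, we will use appropriate statistical methods (for example multiple imputation) to impute missing data", and then: "This will be presented as a sensitivity analysis, i.e. in addition to the complete case analysis".

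**The concern.** Two provisions that are each reasonable fit badly together. The call recovers the AQLQ at a wave where the EQ-5D is also needed, and the economic analysis is then led by complete cases. A participant who answers the call but never returns the pack contributes an interim AQLQ and no interim EQ-5D. Under a complete-case rule for a QALY built from four waves, that person is excluded from the cost-utility result, although baseline EQ-5D, 12-month EQ-5D and record-based NHS costs may all be held.

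The cost-utility analysis serves a stated objective (objective 5 in section 2, listed as secondary in the synopsis). At stake are its precision and how far its analysis set still represents the randomised groups. The companion analysis, cost per 0.5 change in AQLQ, needs no EQ-5D and can keep these participants, so the two economic results could describe different people. The 3-month respondent costs form is in the same postal pack and is not offered on the call either, so some societal cost data would be missing for the same people.

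**Working it through.** **The plan's own figure.** The only stated figure that bears on completeness is the recruitment target (section 8.1, Summary): "Assuming a 10% dropout rate, we will therefore aim to recruit a total sample size of 585 patients". With n/(1 − d) and d = 0.10, 210/0.9 = 233.3, rounded up to 234, and 105/0.9 = 116.7, rounded up to 117. Then 234 + 234 + 117 = 585, which reproduces exactly. The analysable total is 210 + 210 + 105 = 525. The protocol gives no figure for EQ-5D or QALY completeness.

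**Inputs for the check.**
- Starting set: 525, taken as participants with baseline and 12-month EQ-5D.
- p: share of participants per wave whose only response is a telephone mini-AQLQ. The protocol does not give it, so 2% to 20% is assumed, equal across arms and waves.
- No other EQ-5D loss is counted, so the result isolates the effect of the call's content.

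**Formulas.** The fraction f with both interim EQ-5D scores depends on overlap between the waves:
- same people at both waves: f = 1 − p
- independent waves: f = (1 − p)²
- different people at each wave: f = 1 − 2p

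Complete QALY cases = 525 × f. The standard error of a QALY difference is multiplied by 1/√f.

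**Results** (nearest whole person, halves rounded down).

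| Assumed p per wave | Same people | Independent | Different people | Rise in standard error |
|---|---|---|---|---|
| 2% | 514 | 504 | 504 | 1–2% |
| 5% | 499 | 474 | 472 | 3–5% |
| 10% | 472 | 425 | 420 | 5–12% |
| 20% | 420 | 336 | 315 | 12–29% |

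Worked line for p = 10%: 525 × 0.90 = 472.5, 525 × 0.81 = 425.25, 525 × 0.80 = 420. The standard error factors at the two ends are 1/√0.90 = 1.054 and 1/√0.80 = 1.118. By arm, DVD and usual care fall from 210 to 168–189 each, and face-to-face from 105 to 84–94.

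If the EQ-5D were taken on the same call, these participants would keep all four scores and this particular loss would be zero.

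**The case against.** The strongest reply is that the protocol does not say the EQ-5D is lost. The call accompanies a reminder. Nothing closes the wave or refuses a pack returned later. Nor does the protocol say that all four scores are needed for a QALY. A rule for one missing intermediate score may sit in an analysis plan that is not shown. This stands, and it confines the point to people whose only response is the call and to a complete-case rule.

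It can also be said that missing data are already addressed: their extent will be checked, multiple imputation is named, and both results may be reported. That is correct, but the imputation is conditional and ranked second. That ranking is fixed in the protocol itself.

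Finally, keeping one chasing call to the instrument behind the primary outcome is a defensible choice about participant burden. The synopsis also allows recruitment to be extended to reach 525 complete data sets, although it does not say that these include the interim EQ-5D.

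A reader might infer three stronger things that the protocol does not support:
- **All postal non-return is the loss.** Applying an assumed 5–25% non-return per wave, independently and on top of 10% dropout, would give 475 down to 296 complete cases of 585. That counts people who are never reached or are contacted only by email, none of whom a longer call would recover, and it relies on independence between waves.
- **The weight of the interim waves measures the loss.** Under an assumed trapezoid rule the 3- and 6-month scores carry 0.25 + 0.375 = 62.5% of the QALY. A complete-case rule excludes a person for any missing score whatever its weight, and the protocol names no QALY method.
- **The result is biased in a known direction.** The protocol has no evidence that low users of the DVD return fewer forms or that loss differs by arm.

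**Conclusion.** The point holds in a limited form. At 3 and 6 months the telephone fallback yields an AQLQ without an EQ-5D. Combined with complete case as the leading economic analysis, it would remove from the cost-per-QALY result people who are in contact with the trial and may have EQ-5D at both ends of follow-up.

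The size cannot be derived from the protocol. It is negligible at a 2% telephone-only share and material at 20%. The range assumes equal shares by arm and wave, no late postal return, and a QALY that needs all four scores. The direction of any bias is unknown. The primary 12-month AQLQ comparison is untouched. The change is worth making because it is cheap and because answers not asked for on the call may not be recoverable later.

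**What to change.** 1. In section 7, Questionnaire assessments at 3 and 6 months, offer the EQ-5D together with the mini-AQLQ on the telephone call. The 3-month respondent cost items could be added if the length of the call allows.
2. In the Health economic evaluation, make multiple imputation by arm the base case, using observed EQ-5D, AQLQ (including scores obtained by telephone) and costs. Report complete case as the sensitivity analysis.

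The first change recovers only those reached by telephone; the second also covers people who are not. Either helps alone. The first costs a few more questions in a call already being made and a sentence in section 7. The second changes the rank of a method the protocol already names, and puts a missing-at-random assumption into the base case, which should be stated.

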#### 12 months final assessment visit

Subjects will be contacted by telephone or mail to arrange the final visit, which will occur 12 months (±4 weeks) after the initial visit. Participants who do not respond will be sent a single reminder letter and given the option to complete the 12 month questionnaires by post. The study nurse performing the final assessment will be a different staff member from that performing the baseline assessment. They will be blinded to the subject's randomisation group. The assessment will consist of:

- Facilitating subject completion of validated questionnaires: Diseasespecific health status (AQLQ), Nijmegen hyperventilation questionnaire, Asthma Control Questionnaire, generic health status (EuroQOL); anxiety and depression scores (HAD questionnaire), respondent costs questionnaire.
- Clinical details: Smoking status, asthma history, co-morbidities, medication, and exacerbation frequency.
- Physiological measurements: Spirometry (FEV1, FEV1/FVC ratio, PEFR), measured with standardized calibrated portable spirometer; fraction of exhaled nitric oxide (FENO), measured with Aerocrine Mino portable monitor.
- A short questionnaire exploring subject perception of the intervention they received and their experiences of being in the trial

If the trained study nurse makes a clinical assessment of potentially dangerous or unstable asthma, the subject will be referred urgently to their usual primary care asthma clinician.

